3.7 ATRA Dose and Duration in Non-APL AML

There are no clinical studies comparing doses of ATRA in the treatment of APL. The standard dose is 45 mg/m² per day in divided doses, though some reports suggest that a reduced dose of 25 mg/m² is equally effective (Tallman and Altman 2009). Daily dosing of ATRA is typically continued until complete remission (CR) by clinical measures has been achieved, as long as the patient is tolerating treatment well. Patients who have received ATRA for at least two weeks but were discontinued because of toxicity even eventually achieved CR. After the induction of CR, APL patients receive intermittent ATRA for up to 2 years to achieve a molecular remission.

Though very low doses of ATRA in combination with IMG-7289 were needed to induce differentiation in cultured AML cells, higher exposure to ATRA than that needed for differentiation may be required to induce AML cell death (apoptosis) and potentially reduce the leukaemic stem cell pool. Hence, in combination with IMG-7289, the proposed dose of ATRA is 45 mg/m² per day divided into two doses.

The objective of this phase of the study is to expose leukaemic cells to a combination of both IMG-7289 and ATRA. Non-clinical models had suggested the half-life of IMG-7289 was less than 24 hours. The PK parameters now available for the first four dose-finding sub-cohorts indicate a drug half-life of 4-5 days. Thus, what was originally defined as the 7 day “rest” period is one during which patients are still exposed to IMG-7289 at or above the IC₅₀ of the drug. This degree of exposure has, however, been demonstrated to be well tolerated. Thus, to match more closely the exposure of ATRA to IMG-7289, ATRA will be given at the planned dose of 45 mg/m², but for 21 days, followed by a rest period of 7 days. This dosing schedule of ATRA is regarded as safe as it affords less exposure than standard recommended treatment regimens of ATRA for acute promyelocytic leukaemia in which 45-60 days of daily ATRA at 45 mg/m² would be most common.

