At least three patients will enroll in each cohort/sub-cohort, with a minimum of 3 patients per cohort/sub-cohort required to complete the entirety of Cycle 1 (i.e., the applicable IMG-7289 dosing and rest periods). Each dose-finding sub-cohort will include a sentinel patient to be dosed for 7 days, the safety of which will be determined by the DSMC before the remainder of the sub-cohort is treated; duration-finding cohorts will not include sentinel patients. Therefore, with the exception of a sentinel patient in each dose-finding sub-cohort, patients will be enrolled on a rolling basis. As there is no evidence in non-clinical studies of acute toxicity with IMG-7289, even at extremely high doses, it is believed that one sentinel patient for each dose-finding sub-cohort is sufficient to establish the acute safety of IMG-7289 dosed with and without ATRA. Since this study is not

investigating the effects of cytotoxic agents, enrolling patients on a rolling basis facilitates progression to later cohorts that could offer greater therapeutic benefit.

Patients will be treated with IMG-7289 in cycles, each cycle comprised of one IMG-7289 dosing period followed by one rest period. The number of initially allowed IMG-7289 cycles differs by cohort, as does the duration of IMG-7289 dosing. Patients may initially undergo four (Cohort 1), two (Cohort 3/3 χ) or one (Cohort 4/4 χ) IMG-7289 treatment cycles while on study to a total of approximately 28 days of IMG-7289 dosing. During the initially allowed IMG-7289 treatment cycles and regardless of the dosing duration, the rest period will remain at 7 days, unless assessment is made by the DSMC that either a specific patient or an entire cohort could benefit from an extended rest period. This decision could be taken if there is no clear indication of the restoration of normal haematopoiesis in the 7 day period or analysis of the IMG-7289 pharmacokinetic parameters in the earlier sub-cohorts suggest the rest period duration requires adjusting. As IMG-7289 treatment may lead to cytopenias, transfusions may be administered in accordance with standard institutional guidelines.

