8.2.1 IMG-7289 Toxicity Definitions

Haematologic Toxicity: Haematologic values outside of the normal reference range are inherent features of AML and MDS, and are expected effects of many therapeutic attempts to manage these diseases. These effects will not be considered DLTs.

Both genetic knockdown (KD) of LSD1 mRNA and pharmacologic inhibition of LSD1 show that the loss of LSD1 activity arrests the production of mature red cells, platelets and granulocytes while over-producing monocytes (Sprussel *et al.*, 2012; Kerenyi *et al.*, 2013). Production of cells of lymphoid lineage, B and T cells is unimpaired indicating that LSD1 has very cell-specific functions and its inhibition also has very specific effects. LSD1 inhibition in AML cells causes the induction of monocytic differentiation markers, as well as a reduction of self-renewal potential of leukaemic cells, eventually resulting in apoptosis of treated cells. Thus, the anaemia, thrombocytopenia, neutropenia and monocytosis attending LSD1 inhibition, as observed in animals treated with IMG-7289, reflect primary pharmacodynamic effects. The kinetics of anaemia, thrombocytopenia, and neutropenia following complete LSD1 inhibition are a function of the lifespan of the individually affected cell types. Over the course of LSD1 inhibition, platelet and neutrophil counts are the most affected, reflecting their short mean lifespans of approximately seven and twelve days, respectively. Recovery of peripheral counts is reversible, rapid, and temporarily overshoots baseline values. At lower doses, the effects on haematopoiesis are much less pronounced suggesting that a modicum of residual LSD1 activity is sufficient to support some blood cell formation. Thus, both the duration of LSD1 inhibition as well as the degree of inhibition are critical to the pharmacodynamic effects on myeloid lineages.

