The intended dosing plan for high risk AML/MDS patients is predicated on the supposition that LSD1 must be maximally inhibited to achieve the greatest therapeutic benefit. The concentrations of LSD1 inhibitors such as IMG-7289 (free base) used to achieve maximal effects on growth, differentiation and apoptosis *in vitro* with primary patient-derived AML cells as well as AML cell lines are similar to concentrations that *in vivo* inhibit red cell, platelet and granulocyte production. It is therefore expected that high risk AML/MDS patients will require treatment at doses sufficient to induce profound thrombocytopenia and neutropenia. These drug-induced but reversible cytopenias can be managed clinically as needed with platelet and red cell transfusions as well as broad-spectrum antibiotics in the case of febrile neutropenia, as are already standard practices in the routine management of AML/MDS patients receiving intensive SOC chemotherapy.

The effects of IMG-7289 on normal myeloid haematopoiesis observed in non-clinical studies are expected in humans; these are pharmacodynamic effects of LSD1 inhibition by IMG-7289, thus are not regarded as adverse. These events, with the exceptions noted below, will not be considered DLTs.

Dose Limiting Toxicity (DLT): DLT is defined as any one of the following AEs that occurs during the first cycle of therapy and is considered by the Investigator to be possibly, probably or definitely related to IMG-7289.

- A clinically significant bleeding event;
- Any Grade 4 or 5 non-haematologic adverse event;

- Any Grade 3 non-haematologic adverse event with failure to recover to Grade 1 within 7 days of drug cessation, with the following exceptions:
 - ≥ Grade 3 nausea, vomiting or diarrhoea that responds to standard medical care
 - ≥ Grade 3 aesthenia lasting less than 14 days
- Any Grade 3 electrolyte abnormality unrelated to the underlying malignancy and persisting greater than 24 hours.

Patients who experience a dose limiting toxicity (DLT) will have their dose adjusted downward if the Medical Monitor and Principal Investigator deem it safe for the patient to continue on IMG-7289. To ensure a minimum of 3 Cycle 1 completers, and contingent on the number of prior DLTs within the sub-cohort/cohort, such patients may be replaced.

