*All criteria need to be fulfilled; marrow evaluation should be based on a count of 200 nucleated cells in an aspirate with spicules; if ambiguous, consider repeat exam after 5 to 7 days; flow cytometric evaluation may help to distinguish between persistent leukaemia and regenerating normal marrow; a marrow biopsy should be performed in cases of dry tap, or if no spicules are obtained; no minimum duration of response required.
¶In cases with low blast percentages (5-10%), a repeat marrow should be performed to confirm relapse. Appearance of new dysplastic changes should be closely monitored for emerging relapse. In a patient who has been recently treated, dysplasia or a transient increase in blasts may reflect a chemotherapy effect and recovery of haematopoiesis. Cytogenetics should be tested to distinguish true relapse from therapy-related MDS/AML.

Table 15: Response Criteria for MDS

Category	Response Criteria (responses must last at least 4 weeks)
Complete remission	Bone marrow: ≤ 5% myeloblasts with normal maturation of all cell lines* Persistent dysplasia will be noted*† Peripheral blood‡ Hgb ≥ 11 g/dL Platelets ≥ 100 x 10 ⁹ /L Neutrophils ≥ 1.0 x 10 ⁹ /L† Blasts 0%
Partial remission	All CR criteria if abnormal before treatment except: Bone marrow blasts decreased by ≥ 50% over pretreatment but still > 5% Cellularity and morphology not relevant
Marrow CR†	Bone marrow: ≤ 5% myeloblasts and decrease by ≥ 50% over pretreatment† Peripheral blood: if HI responses, they will be noted in addition to marrow CR†
Stable disease	Failure to achieve at least PR, but no evidence of progression for > 8 wks
Failure	Death during treatment or disease progression characterized by worsening of cytopenias, increase in percentage of bone marrow blasts, or progression to a more advanced MDS FAB subtype than pretreatment
Relapse after CR or PR	At least 1 of the following: Return to pretreatment bone marrow blast percentage Decrement of ≥ 50% from maximum remission/response levels in granulocytes or platelets Reduction in Hgb concentration by ≥ 1.5 g/dL or transfusion dependence
Cytogenetic response	Complete: Disappearance of the chromosomal abnormality without appearance of new ones Partial: At least 50% reduction of the chromosomal abnormality

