Disease progression	For patients with: Less than 5% blasts: ≥ 50% increase in blasts to > 5% blasts 5%-10% blasts: ≥ 50% increase to > 10% blasts 10%-20% blasts: ≥ 50% increase to > 20% blasts 20%-30% blasts: ≥ 50% increase to > 30% blasts Any of the following: At least 50% decrement from maximum remission/response in granulocytes or platelets Reduction in Hgb by ≥ 2 g/dL Transfusion dependence

Category	Response Criteria (responses must last at least 4 weeks)
Survival	Endpoints: Overall: death from any cause Event free: failure or death from any cause PFS: disease progression or death from MDS DFS: time to relapse Cause-specific death: death related to MDS

To convert haemoglobin from grams per deciliter to grams per liter, multiply grams per deciliter by 10.

MDS indicates myelodysplastic syndromes; Hgb, haemoglobin; CR, complete remission; HI, haematologic improvement; PR, partial remission; FAB, French-American-British; AML, acute myeloid leukaemia; PFS, progression-free survival; DFS, disease-free survival.

*Dysplastic changes should consider the normal range of dysplastic changes (modification).

†Modification to IWG response criteria.

#Transient cytopenias during repeated chemotherapy courses should not be considered as interrupting durability of response, as long as they recover to the improved counts of the previous course.

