The primary objective, the adequacy of IMG-7289 dose and duration with and without ATRA in producing a pharmacodynamic effect, will be determined using serial blood and bone marrow sampling throughout the course of treatment with responses documented according to revised/modified International Working Group (IWG) Response Criteria – [Cheson *et al.* 2003](#) for AML and [Cheson *et al.* 2006](#) for MDS as described in Protocol Section 16.2. Response is to be assessed each time a bone marrow aspirate or biopsy is performed, with the exception of baseline. All available response data will be listed. The visit overall response per patient, as determined by the Investigator, and recorded on the eCRF, will be listed and summarized for each cohort, using the Efficacy Population.

The best response of each AML patient will be programmatically selected based on the following order: Complete Remission (CR), CR w/Incomplete Recovery (CRi), Morphologic Leukaemia-Free State (MLFS), Partial Remission (PR), Cytogenetic CR (CRc), Molecular CR (CRm), Stable Disease (SD), Resistant Disease (RD), Relapse (Rel), Progressive Disease (PD), Death from Indeterminate Cause (DInd), Death in Aplasia (DiA), and Not Evaluable. The best response of each MDS patient will be programmatically selected based on the following order: Complete Remission (CR), Partial Remission (PR), Marrow CR (CRm), Cytogenetic Response (CyR), Stable Disease (SD), Relapse After CR or PR (Rel), Disease Progression (DP), Failure: Disease Progression (FDP), Survival (Sur), Failure: Death During Treatment (FDDT), and Not Evaluable.

Objective response in AML includes Complete remission (CR), CR with incomplete recovery (CRi), Morphologic leukemia-free state, Partial remission (PR), Cytogenetic CR (CRc), and Molecular CR (CRm) and Stable Disease (SD); while objective response in MDS includes Complete remission (CR), Partial remission (PR), Marrow CR, or Cytogenetic response (CyR) and Stable Disease (SD). Objective response rate (ORR) is the proportion of responders with AML or MDS. ORR and its Fisher exact 95% confidence interval will be presented.

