Additionally, the Kaplan-Meier method will be used to analyze event-free survival (EFS) and overall survival (OS); Summaries will present the number (%) of subjects with events, the number (%) of subjects without events (censored), the median (95% CI) survival, and the probability of 6-month survival. OS is defined as the time interval between treatment start date and death date, and OS will be censored at the last date known alive. EFS is defined as the time interval between the date of treatment start and date of resistance, relapse, progression, or death. For subjects that do not have an event, EFS will be censored at the date of last tumor assessment prior to any concurrent cancer chemotherapy and transfusion.

IX. Safety Analysis

The safety and tolerability of IMG-7289 with and without ATRA will be assessed by the analysis of adverse events (AEs), as well as changes in physical examinations, vital signs, laboratory values and ECGs as detailed below, using the Safety Population.

A. Adverse Events

The AEs reported on the eCRFs will be coded using the latest version of MedDRA available to the sponsor at the time of study initiation (up-versioning will not occur), associating lower-level terms with preferred terms and system organ classes (SOC) by the primary hierarchy. The tables will display counts and percentages of subjects who reported at least one AE in each system organ class represented in the AE data. Within each system organ class, the tables will display the counts and percentages of subjects reporting at least one AE, as designated by the preferred terms.

In any given category (e.g., SOC or preferred term) a patient will be counted only once. If a patient has the same AE on multiple occasions, only the highest toxicity grade will be used. Similarly, only the most related event will be used. Percentages will be based on the number of patients in the subgroup of patients being tabulated and not the number of events. Summaries that are displayed by system organ class and preferred terms will be ordered by descending order of incidence of system organ class and preferred term within each system organ class.

Treatment-emergent adverse events will be summarized. Only those events with an onset date on or after the date on which IMG-7289 was first dispensed, and within 28 days of last IMG-7289 treatment are to be recorded on the AE eCRF; therefore, all reported AEs are expected to be treatment-emergent. However, if eCRF completion

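### SAP VIII.A: if a transfusion alone triggers EFS censoring, only event-free patients are cut back, and the Kaplan-Meier EFS is biased downward

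*SAP*

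**What the plan says.** SAP VIII.A counts resistance, relapse, progression or death as an EFS event and does not require that it precede a transfusion. For patients without an event, "EFS will be censored at the date of last tumor assessment prior to any concurrent cancer chemotherapy and transfusion". The sentence does not say whether either trigger is enough or both are needed. It also does not define a tumor assessment. The nearest definition is earlier in the same section: "Response is to be assessed each time a bone marrow aspirate or biopsy is performed, with the exception of baseline". Under SAP X.D, any transfusion on or after the date of the first dose is concomitant.

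The protocol expects transfusions:

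- Section 5.1: "As IMG-7289 treatment may lead to cytopenias, transfusions may be administered in accordance with standard institutional guidelines".
- Section 8.2.1: drug-induced cytopenias "can be managed clinically as needed with platelet and red cell transfusions". During LSD1 inhibition, "platelet and neutrophil counts are the most affected, reflecting their short mean lifespans of approximately seven and twelve days, respectively".
- Section 6.1.1, inclusion criterion 7: transfusion may be used to reach the platelet entry limit.
- Section 3.7: the rest "period is one during which patients are still exposed to IMG-7289 at or above the" drug's IC50.

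In MDS, Table 15 (Section 16.2) makes transfusion dependence part of relapse ("Reduction in Hgb concentration by ≥ 1.5 g/dL or transfusion dependence") and of disease progression ("Reduction in Hgb by ≥ 2 g/dL Transfusion dependence").

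SAP VIII.A also plans medians and a 6-month probability for EFS and OS, with OS censored when the patient was last known to be alive. Protocol 12.7 and SAP VI.K describe EFS and OS as summaries to be produced if applicable.

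**The concern.** Kaplan-Meier estimation needs censoring that is unrelated to the outcome. Take two patients transfused on Day 10. One progresses on Day 60 and contributes 60 days and an event. The other stays event-free and is cut back to the last assessment before Day 10. The plan treats them differently because of what happened after the transfusion.

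Events stay in the analysis while event-free follow-up is removed. The reported EFS would then understate the drug, and more so where supportive care is used more. Protocol 8.2.1 expects milder effects on blood counts at lower doses, so the distortion may also differ between dose cohorts.

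**Working it through.** **1. Timeline (Protocol Synopsis, Study Duration; Tables 1 and 4).** Day of last initial dose = (dosing days + 7) × (cycles − 1) + dosing days. End of study is 28 days later, and screening adds up to 28 days.

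| Cohort | Last dose | End of study | With screening | Stated |
|---|---|---|---|---|
| 1 | 14×3+7 = Day 49 | Day 77 | 105 d = 15 wk | ~15 wk |
| 3/3χ | 21×1+14 = Day 35 | Day 63 | 91 d = 13 wk | ~13 wk |
| 4/4χ | Day 21 | Day 49 | 77 d = 11 wk | ~11 wk |

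The stated figures are reproduced. Against Day 182, follow-up after the initial cycles covers 77/182 = 42%, 63/182 = 35% and 49/182 = 27%.

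**2. First post-baseline marrow (Schedule 16.1).** Cohort 1: Cycle 2 Day 14 = 14+14 = Day 28. Cohort 3: Cycle 2 Day 21 = 21+21 = Day 42. Cohort 4: Cycle 1 Day 28. The marrow counts in Protocol Section 10 (4, 3 and 3) agree. If only marrow counts as a tumor assessment, an event-free patient transfused before that day is censored at baseline.

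**3. Direction, if either trigger is enough.** Each Kaplan-Meier factor is 1 − d/n. The rule leaves event times and d unchanged and can only reduce n, so no factor can rise. Example: 40 patients, 20 with events at distinct times before Day 77, 20 event-free, and k of the event-free cut back to time 0. The product telescopes to (20 − k)/(40 − k):

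- k = 0: 20/40 = 0.50
- k = 5: 15/35 = 0.43
- k = 10: 10/30 = 0.33
- k = 15: 5/25 = 0.20
- k = 20: 0

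**4. Size.** Every rate here is an assumption. EFS is exponential with median 150 days, so true Day-77 EFS = 2^(−77/150) = 70%. Either 50% or 80% are ever transfused, with median time to first transfusion 14 days, independent of EFS. Of patients event-free at Day 77, 20% leave then; the rest are followed to Day 250. Marrow is at Days 0, 28, 56, 77 and every 28 days after. The simulation used 200,000 patients.

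The share of event-free patients censored at baseline, with a Day 28 marrow, is the transfused share × (1 − 2^(−28/14)): 0.50 × 0.75 = 37% and 0.80 × 0.75 = 60%. With about 16 event-free patients among 40, that is about 6, or 9 to 10.

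| Reading or assumption | Day-77 EFS or bias |
|---|---|
| No transfusion cut | 70% |
| Either trigger, marrow, 50% / 80% transfused | 64% / 58% |
| Either trigger, blood counts every 3 days, 50% / 80% | 64% / 60% |
| Transfusion correlated with poor prognosis (0.4-0.7), 50% / 80% | 2-4 / 7-9 points low |
| All follow-up ends at Day 77, 80% transfused | about 38% |
| Both triggers required, 80% transfused, 5-30% starting chemotherapy | 68.6-69.9% vs 70.1% (0.2-1.5 points low) |
| Cut also applied to events after transfusion, independent, 50% / 80% | 67% / 63% |
| Same, correlation 0.4, 50% / 80% | 75% / 72% |

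With 40 patients the sampling SD of the Day-77 estimate is about 7 points.

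**5. Check of the fix.** Suppose 30% start new therapy (median 90 days, unrelated to prognosis). Cutting all patients alike gives 69.8%, counting everything gives 70.1%, and cutting only event-free patients gives 68.8%.

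**The case against.** The strongest reply is that both direction and size depend on how the sentence is read. If both triggers are needed, the effect is negligible. If programmers also cut events that follow a transfusion, EFS can come out too high. This stands: the downward bias belongs to the either-trigger reading. That is the more natural reading, but it is not the only one. The disagreement between readings is itself a reason to rewrite the sentence.

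The size is also open to challenge. The 6-12 points assume that transfusion is independent of prognosis, and a realistic correlation reduces them. Table 14 lets AML non-responders count as resistant soon after initial treatment, which a smooth exponential curve does not represent. Both points stand. Shorter follow-up pushes the other way.

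A reader might infer that the rule censors MDS patients whose transfusion dependence is the event. The documents do not support that. Response is determined by the Investigator, and dependence recorded as relapse or progression is an event, so the censoring sentence does not apply. Only an explicit statement is missing.

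A reader might also infer that 6-month OS is biased upward because follow-up stops too soon. This is not established. Protocol Section 9 is redacted, OS censoring is not tied to the end-of-study visit, and additional cycles are open-ended. The readable schedule shows no survival visit, so a query is fair. Whether permitted hydroxyurea counts as concurrent chemotherapy likewise cannot be settled from the readable text.

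**Conclusion.** The concern holds for EFS, conditionally. If a transfusion alone triggers the cut, censoring depends on the outcome and the EFS curve is biased downward. That direction follows from the arithmetic and not from the assumed rates. The size does rest on them: roughly 6-12 points at Day 77 under independence and 2-9 points if sicker patients are transfused more, for a true 70%, 20% leaving at Day 77 and 50-80% transfused early. The lower values are within the sampling SD for 40 patients.

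It would be too strong to say that the planned EFS is certainly too low or that these figures predict the error, because the documents give no transfusion or event rates. The 6-month point is a query only. EFS and OS are if-applicable summaries that drive no dose decision, so severity is minor to moderate.

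**What to change.** In SAP VIII.A, before database lock:

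- Delete the words *and transfusion*, and state that a transfusion alone does not censor.
- Choose one rule for everyone: censor all patients alike at the last disease assessment before new anti-leukaemia therapy, or count all events and follow-up regardless of new therapy.
- Say which assessment counts as a tumor assessment (marrow only, or blood counts as well).
- State that transfusion dependence recorded as MDS relapse or progression under Table 15 remains an EFS event.

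This costs two deleted words and a few added sentences, with no new data.

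Query to the sponsor: are vital status and disease status collected to 6 months for all treated patients? If so, show numbers at risk. If not, do not report the 6-month EFS and OS probabilities as planned, and show numbers at risk for what is reported. Dropping them costs nothing. Collecting vital status instead means one query for each of about 40 patients and, if Section 9 does not already provide for it, a short amendment; a 6-month EFS would also need disease status.
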